6. DATA COLLECTION AND ANALYSIS

6.1 Effectiveness:

A statistical analysis based on analysis of variance will be carried out. Given that this is an early-stage observational study, with a small population size, the analysis may not provide appropriate power and significance of endpoint measurements. Standard statistical analysis including the number of observations, mean, ranges for quantitative variables and relative percent for some categorical variables will be reported as appropriate.

During and at the end of the trial stage, patients will be asked to provide feedback regarding sensations and pain relief as a result of the polymodal stimulation therapy and in comparison with conventional therapy.

Pain intensity will be rated using the numerical pain rate scale (NPRS). Patients will score the severity of pain using this 11-point scale, with zero (0) indicating no pain and ten (10) indicating the worst pain imaginable. The patient will be asked to evaluate the average level of pain experienced during a particular time window between visits. The primary endpoint of record will correspond to the average NPRS score reported at the end of each therapy period. Patients will serve as their own control.

6.2 Paresthesia, Patient Impression, and Satisfaction

At the end of the trial period, patients will also be asked about their paresthesia experience, therapy preference, and their global impression of improvement and satisfaction. Questionnaires will be administered for such effects.

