5. DESIGN AND PROCEDURES

5.1 Study Design

This is a prospective, observational cross-over study that will compare conventional SCS and polymodal SCS during two different time windows during an SCS trial period. Up to 25 patients will be included in the study. Figure 1 illustrates a general diagram of the study process. A screening/enrollment visit will assess the eligibility of a potential subject who has already given adequate time to evaluate and discuss the informed consent form. Patients that meet all the inclusion and exclusion criteria and who reaffirm voluntary informed consent to participate in the study will be enrolled. Patients enrolled in the study will visit the clinic to start the SCS trial period which involves the implantation of the stimulation leads and programming of conventional SCS therapy. Conventional SCS therapy will be administered before PM-SCS therapy for 4 ± 1 days. [REDACTED]

[REDACTED]

[REDACTED]

[figure not shown]

Figure 1. Flow diagram of the study process.

After the patient has trialed conventional SCS therapy, there will be a washout period which is expected to last no more than one day. This will allow analgesic effects of the conventional therapy to wear off. The patient will visit the clinic to crossover to PM-SCS therapy and will trial it for 4 ± 1 days. After the trial period is over, the implanted temporary leads will be disconnected from the ENS and removed from the patient and the trial period will end. The trial period during the study will not extend longer than ten days. Table 2 shows a schedule of events.

Table 2. Schedule of Events.

Event\Activity	Enrollment/ Baseline (Day 0)	Start of SCS Trial (0-30 days after enrollment/baseline)	Crossover to Polymodal SCS (3-5 days after start of trial)	End of Study (3-5 days after crossover to PM-SCS)
Informed Consent	X			
Inclusion/Exclusion Criteria	X			
Pregnancy Test^A	X			
General Health and Pain Medications	X			
Pain NPRS	X		X	X
Informed Consent Reaffirmation	X			
Lead Implantation		X		
X-ray Fluoroscopy		X	X	X
Programming of Conventional SCS and start of trial		[X]		
Programming of PM- SCS			[X]	
Stimulation Sensation Assessment				X
Impression of Improvement and Patient Satisfaction				X
Adverse Event Assessment		X	X	X

^A Administered only to subjects of childbearing potential

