Accordingly, follow up phone visits will be performed as needed during the study. After the first day of therapy and depending on the extent of pain relief reported by the patient, the CFT may instruct the patient to adjust the level of stimulation as deemed appropriate by patient to obtain optimum pain relief. The patient may also be instructed to use a different therapy group in case a therapy cannot be optimized with the previously tried therapy group. This process may be repeated during trial days for both the conventional SCS part of the trial and the PM-SCS part of the trial. Depending on feedback from the phone visits, the PI may decide to schedule a visit to the clinic for reassessing lead position and reprogramming, or to address an adverse event.

5.7 Optional unscheduled clinic visit:

If lead migration is suspected, the PI may schedule a reprogramming visit. In this visit, the PI may evaluate the position of the leads inside the epidural space using x-ray fluoroscopy and reposition and/or reprogram as needed. The PI may also change stimulation parameters using patient feedback as done during the initial visit or during the crossover visit. This visit may also be used to address any other mild or moderate adverse events related to SCS therapy.

5.8 Clinic Visit 4: End of trial period visit:

The patient will return to the clinic as scheduled for an end of trial period visit, in which the stimulation will be stopped, the hardware disconnected from the leads, and the temporary leads removed. Before stimulation is stopped, the patient will be asked to provide feedback about pain status, subjective satisfaction, and paresthesia sensation, which will be recorded in the appropriate CRFs (CRF06, CRF07, and CRF08). This visit may take place any time if the PI deems necessary to exit a patient from the trial and study, or if the patient voluntarily decides to withdraw.

5.9 Other therapies:

As per standard of care practice the patient may continue on prophylactic antibiotics as prevention for bacterial skin infection. Patient will also follow the investigating physician's protocol for anticoagulant therapy, other medications, as well as over-the-counter medications and supplements.

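### Sensation under conventional SCS is to be compared with PM-SCS, but no sensation, impression or satisfaction rating is scheduled while conventional SCS is in use

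*Combined protocol and SAP*

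**What the plan says.** Section 6.1 (Effectiveness) says that patients will be asked for "feedback regarding sensations and pain relief as a result of the polymodal stimulation therapy and in comparison with conventional therapy". It places this both while the trial stage is in progress and at its close.

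Section 6.2 gives a single time point: "At the end of the trial period, patients will also be asked about their paresthesia experience, therapy preference", followed by global impression of improvement and satisfaction.

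The schedule of events appears twice, in the Protocol Summary and as Table 2 in section 5.1. In both, the rows "Stimulation Sensation Assessment" and "Impression of Improvement and Patient Satisfaction" carry one mark each, in the End of Study column. The NPRS row is marked at baseline, at crossover and at End of Study.

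Section 5.8 (Visit 4) matches the schedule: "Before stimulation is stopped, the patient will be asked to provide feedback about pain status, subjective satisfaction, and paresthesia sensation". The answers go on CRF06 to CRF08. Section 5.5 (Visit 3, the end of conventional SCS) has the pain level under conventional SCS recorded on CRF05 and names no other patient-reported form.

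**The concern.** Section 6.1 asks for a comparison of sensations between the two therapies, yet the forms are completed only while PM-SCS is running. Nothing is scheduled that captures how conventional SCS felt while the patient was using it.

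Sensation matters in this study. Section 5.4.1 programs conventional SCS to elicit paresthesia, and section 1.1 notes that newer modalities may relieve pain without paresthesia that is often uncomfortable. If PM-SCS is rated as it runs and conventional SCS is rated from memory, the two ratings are not collected on equal terms. The design is open label and every patient receives conventional SCS first, so the recalled therapy is the same one in every patient and sequence cannot balance any recall or recency effect.

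**Working it through.** The plan states no sample-size, power or alpha figure that bears on this point. The check sets the sections side by side and works out the recall interval.

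**1. What is scheduled at the end of each therapy**

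| Item | End of conventional SCS (Visit 3) | End of PM-SCS (Visit 4) | Source |
|---|---|---|---|
| Pain NPRS | yes (CRF05) | yes | both schedules; 5.5, 5.8 |
| Stimulation sensation | no | yes | both schedules; 5.8, 6.2 |
| Impression and satisfaction | no | yes | both schedules; 5.8, 6.2 |
| Therapy preference | no | yes | 6.2 |

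On sensation, impression and satisfaction, each patient has 0 scheduled ratings at the end of conventional SCS and 1 at the end of PM-SCS.

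**2. Does any other text supply the missing rating?** Section 6.1 speaks of feedback during the trial stage but attaches no visit, form or instrument to it. The phone contacts in section 5.6 are made as needed, to follow and adjust therapy, and carry no questionnaire.

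**3. Which items are meant to be compared?** The comparison sentence in section 6.1 covers sensations and pain relief. Pain has its own score at the end of each therapy period. Sensation does not. For global impression and satisfaction, the visible text says only that patients will be asked.

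**4. Time from the end of conventional SCS to the forms.** Inputs: washout of 0 to 1 day (5.1, 5.5), and End of Study 3 to 5 days after crossover (both schedules).

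- Washout inside the 3-5 day window: 3 to 5 days.
- Washout before the window: 0 + 3 = 3 days at the least, 1 + 5 = 6 days at the most.
- PM-SCS itself: 0 days, because section 5.8 asks before stimulation is stopped.

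Section 5.1 caps the trial period at ten days. The longest windows sum to 5 + 1 + 5 = 11 days, so the cap and the windows need to be reconciled. The 6-day gap is still possible within the cap when conventional SCS lasts 4 days: 4 + 1 + 5 = 10.

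**5. What happens to the conventional rating at Visit 4?** The form wording is not visible, so there are two cases.

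- The form asks about both therapies: a conventional rating exists, but it is recalled over the interval in step 4.
- The form asks only about the current therapy: there is no conventional rating and no within-patient comparison on that form.

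Only one case can hold for a given form. In neither is there a contemporaneous rating of conventional SCS.

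**6. With the forms at Visit 3.** Under the order in section 5.5 (assessment, then washout), the conventional gap falls to 0 days. If washout comes before the visit, as section 5.1 can be read, it is at most 1 day. Up to 25 patients would then give up to 25 near-contemporaneous pairs.

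**The case against.** The strongest case against is that this is an early feasibility study, that section 6.1 itself concedes limited power, and that these outcomes are supportive with no visible inferential analysis. The primary endpoint, sample size and safety are untouched. The NPRS also asks for average pain over a period between visits, so the study already relies on recall over days. All of this is fair, and it keeps the point to a worthwhile improvement. The NPRS parallel goes only so far: its score for conventional SCS is taken when that therapy ends, not after the other has been tried.

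Several stronger readings are tempting, and the documents do not support them.

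- A reader might infer that the main comparison of the two therapies rests on recall. It does not. NPRS is scored at the end of each therapy period.
- A reader might infer that the plan sets out to compare satisfaction and global impression between therapies. The visible text plans a comparison only for sensations and pain relief.
- A reader might conclude both that conventional SCS is rated from memory and that no paired ratings exist. These exclude each other for any one form, and the wording that would decide between them is not available. The appendices and some text after the primary endpoint are redacted.
- A reader might treat the timing of the preference question as a fault. Preference can only be asked once both therapies have been tried.

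**Conclusion.** The point holds in limited form. Section 6.1 seeks a comparison of sensations that the schedules and sections 5.5, 5.8 and 6.2 do not support with any contemporaneous rating of conventional SCS. The same gap exists for impression and satisfaction, and it matters there only if those items are to be compared between therapies.

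The conventional experience is either recalled about 3 to 5 days after it ended (up to 6 if washout precedes the 3-5 day window), against 0 days for PM-SCS, or not collected at all. Recency and expectation would plausibly favour PM-SCS, but the size of any bias cannot be derived from the documents.

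The scheduling gap is plain in the text. Its consequence depends on form wording that cannot be seen. The assignment of CRF07 and CRF08 to satisfaction and sensation is also only inferred from list order in section 5.8. The primary NPRS endpoint is not affected.

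**What to change.** - In both schedules and in sections 5.5 and 6.2, add the sensation assessment at Visit 3, with the conventional NPRS and before PM-SCS programming.
- Do the same for the impression and satisfaction items if they are to be compared between therapies. If not, say so in section 6.2.
- Leave any preference or between-therapy items off the Visit 3 form. Keep therapy preference at Visit 4 only.
- Repeat the same forms at Visit 4 and report within-patient differences descriptively.
- Reconcile section 6.1 with the schedules by naming the visit at which feedback during the trial stage is collected.

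The cost is a few minutes per patient at an existing visit, and possibly a small form edit if the current forms contain comparative items. No new visit or change in sample size is needed. Conventional ratings not collected at crossover cannot be recovered later.

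The change removes the recall asymmetry only. PM-SCS is still always second and open label, so order and expectation effects remain in any Visit 3 to Visit 4 difference and should be stated when it is reported.

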6.3 Safety

Adverse events (AE) related to the stimulation therapies will be tracked during the study period to address any safety outcomes. Any AE encountered using the conventional SCS therapy will also be noted in the patient's medical history. All device and/or procedural adverse events will be reported.

AEs will be tracked and categorized by the PI as related to implant (leads) or activation of the stimulation program. It is expected that the polymodal SCS will have a safety profile similar to conventional SCS.

All AEs will be recorded in the corresponding Case Report Form (CRF). The PI will also rate the AE in terms of its severity. Any AE considered by the PI to be a serious adverse event (SAE) will be reported immediately (within 24 hours) to the sponsor and to the IRB within five (5) days after the PI first learns of the event.

6.3.1 Adverse Events (AEs):

The following is a list of potential adverse events associated to SCS therapy and the indwelling leads with reported risk and frequency of occurrence:

- Related to Lead implant:
 - Movement of lead (possible, 13.2%)
 - Malfunction or failure of lead (possible, 9.1%)
 - Superficial site infection (possible, 4.5%)
 - Complications related to implantation procedure including infection; fever (possible, 3.4%)
 - Persistent or temporary pain at the implant site (unlikely, 1.8%)
 - Tissue reaction to leads (unlikely, 0.3%)
 - Hematoma (unlikely, 0.3%)
 - Bleeding (unlikely, 0.3%)
 - Skin erosion over the leads (unlikely, 0.2%)
 - Allergic reactions to leads (very unlikely, 0.1 %)
 - Paralysis (very unlikely)
 - Nerve injury (very unlikely)
 - Death (very unlikely)
- Related to stimulation:
 - Malfunction of stimulation system (possible, 4.5%)

- Undesirable sensations (possible, 2.4%)
- Increased pain (possible)
- Uncomfortable stimulation of tissue around the leads (possible)
- Development of pain symptoms in a new location (possible)
- Increase in pain intensity, duration, or frequency (unlikely)
- Seizure (very unlikely)
- Paralysis (very unlikely)
- Nerve injury (very unlikely)
- Death (very unlikely)

AEs related to stimulation with the trialed therapy are expected to be comparable to those associated to others encountered with other SCS therapies (such as HF-10 or Burst) or ENS.

At each evaluation the PI will determine whether any AE have occurred, keeping in mind that an AE is any undesirable medical occurrence in the patient. If it is determined that an AE has occurred, the PI should obtain all information required to complete the AE form of the CRF (CRF09). Patients should also be encouraged to contact the PI if any significant AEs occur between visits.

6.2.2 Serious Adverse Events (SAEs):

All serious SAEs must be reported to the sponsor (or designee) and IRB within 24 hours after the PI first learns of the event and to the IRB within 5 days after the PI first learns of the event. An adverse event is considered serious if:

- Leads to death
- Leads to a serious deterioration of the health of the patient that results in:
 - Life-threatening illness or injury
 - Permanent impairment of a body structure or body function

- Inpatient hospitalization or prolongation of existent hospitalization
- Medical or surgical intervention to prevent permanent impairment to body structure or body function

All SAEs will be followed until the event is resolved. The PI will decide if additional follow up information is needed in case the event is not resolved at study completion. In case of death, all possible information available, e.g. autopsy or other post-mortem findings, including the possible relationship to the procedure or treatment should be provided.

6.2.3 Unanticipated adverse device effects (UADEs):

Unanticipated adverse device effects are defined as serious adverse effect on health or safety, or any life-threatening problem or death caused by, or associated with a device, if that effect, or problem, or death was not previously identified in the protocol.

The PI must submit to sponsor (or designee) any UADE within 24 hours after the PI first learns of the effect. The PI must also report the UADE to the IRB according to local regulations.

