Programming with PM-SCS will occur during the trial stage period after the patient has undergone a trial of the therapy using conventional SCS. PM-SCS will utilize the same trial leads, interface trial cable, and remote controller that had been used during the conventional SCS period. The leads, interface trial cable and remote controller are commercial products (i.e. FDA approved). The ENS for PM-SCS is an investigational device based on a commercial platform which has been modified and tested to safely provide programs and therapy groups with the proper parameter sets (F, PW, A). The patient will try conventional SCS therapy at the beginning of the trial stage period for up to five days and then, after a brief washout period, will receive PM-SCS therapy for up to five days.

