Type of Risk	Level of Risk	Risk and Occurrence
Lead Implant Risks	Possible	Lead migration (13.2%) Failure/malfunction of leads (9.1%) Superficial site infection (4.5%) Procedure complications, including infection & fever (3.4%)
	Unlikely	Persistent pain at lead implant site (0.9%) Temporary pain at implant site (0.9%) Tissue reaction to leads (0.3%) Epidural hematoma (0.3%) Skin erosion around the leads (0.2%)
	Very Unlikely	Allergic reaction to leads (0.1%) Paralysis (0.003%) Nerve injury Death
Stimulation Risks	Possible	Malfunction of stimulation system (4.5%) Undesirable sensations (2.4%) Increased pain in area other than implant site Uncomfortable stimulation of tissue around leads Development of pain in a new location
	Unlikely	Increase in pain intensity, duration, or frequency
	Very Unlikely	Seizure Paralysis Nerve injury Death

2.2 Benefits:

Because of the short-term of the study, there is no opportunity for long-term benefits to patients in this study beyond those associated with the outcome of the trial of conventional SCS therapy. A patient that experiences a successful outcome with trialing conventional SCS therapy

will be eligible for a permanent implant. Participation in this study will provide information that will add to our understanding of treatment options for patients with back pain.

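### The UADE definition turns only on whether an effect is named in the protocol, so seizure, paralysis, nerve injury or death from the investigational stimulator would, read literally, not be classed as unanticipated

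*Combined protocol and SAP*

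**What the plan says.** Section 6.2.3 defines a UADE as a grave effect on health or safety, a threat to life, or a fatality, caused by or associated with a device, "if that effect, or problem, or death was not previously identified in the protocol". No other condition is attached.

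Section 6.3.1 opens its list with "The following is a list of potential adverse events associated to SCS therapy and the indwelling leads with reported risk and frequency of occurrence". The part of that list on stimulation includes these entries (closing brackets omitted): "Seizure (very unlikely", "Paralysis (very unlikely", "Nerve injury (very unlikely" and "Death (very unlikely". Table 1 names the same four in its stimulation rows, and the text of section 2.1 names them as very unlikely results of stimulation.

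Section 1.3 states that "The ENS for PM-SCS is an investigational device based on a commercial platform". Section 7.3 confirms that conventional SCS uses the commercial unit and PM-SCS a modified one.

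Reporting times are in sections 6.3, 6.2.2, 6.2.3 and 8.5. (The last two subsections of 6.3 are numbered 6.2.2 and 6.2.3.)

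**The concern.** A UADE category exists to pick out serious device effects that go beyond what the protocol led people to expect. Here the filter is only whether the effect has been named, and the risk sections name the four gravest possible effects of stimulation. The definition says it covers deaths and threats to life, but the list takes out deaths and the most serious injuries attributed to stimulation.

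The stimulator for PM-SCS is the investigational element of the study, so it is the device for which this judgement matters most. At stake is how such an event is labelled: whether anyone records it as unanticipated, whether the UADE report to the IRB under 6.2.3 is made, and whether the final UADE count can be trusted. Because the clause gives no criterion beyond naming, two people applying it could also class the same event differently, one by its letter and one by judgement.

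**Working it through.** The plan gives no figure on this point, so the check sets the passages side by side.

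**1. The test in 6.2.3.** An event is a UADE if it is (a) serious, life-threatening or fatal, and (b) caused by or associated with a device, and (c) an effect the protocol has not already identified. Condition (c) does not mention severity, frequency, mechanism or which stimulator was in use.

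**2. What the protocol identifies under stimulation.**

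| Effect | Section 2.1 text | Table 1, stimulation rows | Section 6.3.1, stimulation list | Rate given for stimulation |
|---|---|---|---|---|
| Seizure | named | named | named | none |
| Paralysis | named | named | named | none |
| Nerve injury | named | named | named | none |
| Death | named, no cause | named, no cause | named, no cause | none |

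The stimulation part of Table 1 has ten entries and so does that of 6.3.1. In each, only two carry a rate: system malfunction (4.5%) and undesirable sensations (2.4%). None of the four effects above does.

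**3. Whether the list could be confined to the commercial device.** It could not. The 6.3.1 list is introduced as covering SCS therapy in general. Section 2.1 says the risks of the study are the same as those of approved commercial systems, and 6.3.1 expects stimulation events with the trialed therapy to be comparable to those of other SCS therapies. The list therefore applies to PM-SCS as well.

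**4. Applying the test.** Take a paralysis caused by the PM-SCS stimulator. Conditions (a) and (b) are met. Condition (c) fails, because paralysis is already identified. It is not a UADE. The same holds for seizure, nerve injury and death, and the result does not change if a second or third case follows.

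**5. Whether another passage repairs this.** The only other UADE rule is in 8.5. It sets reporting times and does not widen the definition.

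**6. What happens to the event instead.** Condition (a) already requires seriousness, so these events would ordinarily meet the SAE definition in 6.2.2.

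| | To the sponsor | To the IRB |
|---|---|---|
| SAE | 24 hours (6.3, 6.2.2, 8.5) | five days (6.3, 8.5); 6.2.2 gives both 24 hours and five days in one sentence |
| UADE | 24 hours (6.2.3, 8.5) | per local regulations (6.2.3); five days (8.5) |

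The sponsor hears equally fast either way, and the IRB is told either way. What drops out is the UADE label, the separate UADE report to the IRB that 6.2.3 requires, and the event's place in the UADE count.

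**The case against.** The strongest reply is that little follows in practice. SAEs and UADEs share one line in 8.5 with the same times, and the visible text attaches no review, pause or other step to a UADE alone. The investigator also relates each event to leads or to stimulation and rates its severity (6.3), and must follow every SAE to resolution (6.2.2). This stands: the loss is one of classification, and the point should be read at that size.

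A second reply is that the 6.3.1 list comes with likelihoods, so an effect is identified only at its stated likelihood, and a sensible investigator would treat a clear excess as unanticipated. That is a reasonable way to run the study, but 6.2.3 does not say it, and with no stimulation rate for any of the four effects there is only a verbal band to judge against.

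Third, parts of section 2.1 and the appendices are redacted and CRF09 is not visible. Redacted text cannot un-list the named effects, but CRF09 may already hold an expectedness field.

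There are also stronger readings that a reader might infer and that the documents do not support:

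- **That grave effects of the stimulator can never be UADEs.** A serious effect that is not listed still qualifies, and a death arising from one could be reported through that effect.
- **That such events would go unreported.** The SAE route and the general reporting rule in 6.3 prevent this.
- **That the misclassification can be sized from Table 1.** The entry "Paralysis (0.003"%) stands in the lead-implant rows. Setting one case in 25 patients (1/25 = 4%) against it would compare a stimulation event with a lead-implant rate.
- **That the listed hematoma and bleeding widen the problem.** They are lead-related, the leads are commercial products, and they say nothing about the stimulator.
- **That a count of zero UADEs would establish the expected similarity to conventional SCS.** Nothing visible makes the UADE count a safety endpoint. The narrower point is that the count could not be relied on.

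**Conclusion.** The point holds as a defect in a definition. By its plain wording, section 6.2.3 keeps stimulation-related seizure, paralysis, nerve injury and death out of the UADE category for the investigational stimulator, whatever their severity or frequency, and no visible passage corrects this. Its size is four named effects, all among the gravest listed, with loss of the unanticipated classification, of the UADE report to the IRB under 6.2.3, and of a reliable UADE count. Expedited reporting to the sponsor is unaffected, and the IRB still receives an SAE report.

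This rests on two assumptions: that the clause is applied as written, and that the redacted text contains no second definition. It is a modest point, but worth correcting because the change is small and the rule as written would misclassify the events for which the category matters most.

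**What to change.** Reword 6.2.3 so that an effect is unanticipated if the protocol did not previously identify it in nature, severity or frequency. Have the investigator record that judgement for each SAE, adding a field to CRF09 only if the form does not already capture it. Since the stimulation entries give no rates for the four effects, frequency will have to be judged against the stated likelihood band, and the sentence should say so.

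In the same edit, reconcile the IRB reporting times: 6.2.2 gives two for SAEs, and 6.2.3 and 8.5 differ for UADEs.

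The cost is one reworded sentence and at most one form field. Treatment, visits and sample size do not change. The downside is that some more events may be classed as UADEs; the documents give no basis for estimating how many.
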